1.0 TRIAL SUMMARY

[figure not shown]
Abbreviated Title	Neoadjuvant pembrolizumab for resectable early stage gastroesophageal adenocarcinoma
Trial Phase	IIa
Clinical Indication	Resectable cT1b-2N0M0 gastroesophageal adenocarcinoma
Trial Type	Prospective clinical trial
Type of control	Historical controls
Route of administration	Intravenous
Trial Blinding	None
Treatment Groups	1
Number of trial participants	33
Estimated enrollment period	24 months
Estimated duration of trial	36 months
Duration of Participation	Until 5 years post-surgical resection, death, or study closure
Estimated average length of treatment per patient	8-11 weeks (pembrolizumab IV q 3 weeks x 3 cycles followed by surgery within 8-11 weeks from first dose of pembrolizumab)

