Pembrolizumab may be interrupted for situations other than treatment-related AEs such as medical / surgical events or logistical reasons not related to study therapy. Participants should be placed back on study therapy within 2 weeks of the scheduled interruption, unless otherwise discussed with the P.I. The reason for interruption should be documented in the patient's study record. If there is any delay in pembrolizumab that would result in patient being unable to undergo surgery within 56-77 days of study initiation (day of first pembrolizumab dose), then patient will go off trial and go directly to surgery.

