6.5 Participant Withdrawal/Discontinuation Criteria

Participants may discontinue study treatment at any time for any reason or be dropped from the study treatment at the discretion of the treating investigator should any untoward effect occur. In addition, a participant may be discontinued from study treatment by the treating investigator or the P.I. if study treatment is inappropriate, the trial plan is violated, or for administrative and/or other safety reasons. Specific details regarding procedures to be performed at study treatment discontinuation are provided in [Section 8.1.4 – Other Procedures](#).

A participant must be discontinued from study treatment but continue to be monitored in the study for any of the following reasons:

- The participant or participant's legally acceptable representative requests to discontinue study treatment
- Confirmed radiographic disease progression outlined in [Section 8.1.2.5.1](#)
- Any progression or recurrence of any malignancy, or any occurrence of another malignancy that requires active treatment
- Unacceptable adverse experiences as described in [Section 6.2.2](#).
- The participant has a medical condition or personal circumstance which, in the opinion of the treating investigator and/or P.I., placed the participant at unnecessary risk from continued administration of study treatment.
- The participant has a confirmed positive serum pregnancy test
- Noncompliance with study treatment or procedure requirements
- Recurrent Grade 2 pneumonitis
- The participant is lost to follow-up
- Administrative reasons

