6.7 Clinical Criteria for Early Trial Termination

Early trial termination will be the result of the criteria specified below:

1. Quality or quantity of data recording is inaccurate or incomplete with $\geq 10\%$ of data unavailable.
2. Poor adherence to protocol and regulatory requirements
3. Incidence or severity of adverse drug reaction in this or other studies indicates a potential health hazard to participants
4. Plans to modify or discontinue the development of the study drug
5. If patient deaths or excessive toxicity attributed to the investigational drug are seen in the 30 days following surgery. A **30-day post-operative** death rate of $\geq 5\%$ attributed to study agent is considered unacceptable. The relationship of the investigational drug to the mortality will be determined by the treating medical oncologist and surgeon.

In the event of Merck decision to no longer supply study drug, ample notification will be provided so that appropriate adjustments to participant treatment can be made.

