7.0 TRIAL FLOW CHART

7.1 Study Flow Chart

Pre-treatment research biopsy for pathologist review	X								
Pre-treatment biopsy for biomarker analysis ^c	X								
Resected surgical specimen for pathologist review						X			
Resected surgical specimen for biomarker analysis ^{c,d}						X			
Foundation One CDx	X					X ^d			
Guardant 360 ctDNA collection and blood banking ^l	X				X		X		X ^k
Stool collection	X				X		X		X ^k

^aCT scan of chest/abdomen/pelvis with IV and PO contrast, OR MRI of abdomen/pelvis plus non-contrast chest CT if contraindication to iodinated dye.

^bOnly needed in women of childbearing potential

^cBiomarker analysis includes testing for MSI via immunohistochemistry (IHC), HER2 testing (via IHC and/or fluorescence in situ hybridization (FISH)), Epstein-Barr encoding region in situ hybridization (EBER ISH), PD-L1 CPS testing, and whole-exome RNAseq expression

^dWill only be able to be performed if there is residual tumor left in surgical specimen

^eSurveillance visits with physician (or nurse practitioner or physician assistant) will occur every 3 months until year 3 post surgery, and then every 6 months until year 5 post surgery

^fSurveillance imaging will be performed annually for 2 years post-surgery and then as clinically indicated

^gWill only be performed as needed

^hWill be checked every 3 months until year 3 post surgery, and then every 6 months until year 5 post surgery

ⁱTSH only be checked, and FT4 and T3 only checked reflexively if TSH is abnormal, per routine care.

^jPatients will come off study 5 years post-surgery, if cancer recurs, or if patient withdraws consent. However, overall survival follow-up will continue to year 5 if cancer recurs or if patient withdraws consent from treatment but not follow up.

^kWill only be collected if patient's gastroesophageal cancer recurs

^lBlood Banking collected and processed per IRB16294A (see [Section 8.1.2.6](#) of this protocol).

^mEndoscopy must be conducted at enrolling institution (see [Section 8.1.2.6.2](#) of this protocol).

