8.1.5.3.2 Follow-up Visits

Subjects who discontinue trial treatment for a reason other than disease progression will move into the Follow-Up Phase and should continue surveillance per standard of care. This includes

physician visits with labs (CEA and CA 19-9) every 3 months until year 3 post surgery and then every 6 months until year 5 post surgery as well as CT scan of chest/abdomen/pelvis with IV/PO contrast (or MRI abdomen/pelvis plus noncontrast chest CT if iodinated dye cannot be administered) annually for 2 years and then on an as needed basis.

Every effort should be made to collect information regarding disease status until the start of new anti-neoplastic therapy, disease progression, death, or end of the study. Information regarding post-study anti-neoplastic treatment will be collected if new treatment is initiated.

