- All AEs meeting serious criteria, from the time of treatment allocation/randomization through 90 days following cessation of study treatment, or 30 days following cessation of study treatment if the participant initiates new anticancer therapy, whichever is earlier must be reported by the investigator.
- All pregnancies and exposure during breastfeeding, from the time of treatment allocation/randomization through 120 days following cessation of study treatment, or 30 days following cessation of study treatment if the participant initiates new anticancer therapy must be reported by the investigator.
- Additionally, any SAE brought to the attention of an investigator at any time outside of the time period specified above must be reported immediately by the investigator if the event is considered to be drug-related.

Investigators are not obligated to actively seek AE or SAE or other reportable safety events in former study participants. However, if the investigator learns of any SAE, including a death, at any time after a participant has been discharged from the study, and he/she considers the event to be reasonably related to the study treatment or study participation, the investigator must promptly notify Merck.

8.2.1 Definition of an Overdose for This Protocol and Reporting of Overdose to the Principal Investigator and to Merck

For purposes of this study, an overdose of pembrolizumab will be defined as any dose of 1,000 mg or greater (≥ 5 times the indicated dose). No specific information is available on the treatment of overdose of pembrolizumab. In the event of overdose, the participant should be observed closely for signs of toxicity. Appropriate supportive treatment should be provided if clinically indicated.

If an adverse event(s) is associated with (“results from”) the overdose of a Merck product, the adverse event(s) is reported as a serious adverse event, even if no other seriousness criteria are met.

If a dose of Merck’s product meeting the protocol definition of overdose is taken without any associated clinical symptoms or abnormal laboratory results, the overdose is reported as a non-serious Event of Clinical Interest (ECI), using the terminology “accidental or intentional overdose without adverse effect.”

All reports of overdose with and without an adverse event must be reported within 24 hours to the P.I. and within 2 working days hours to Merck Global Safety. (Attn: Worldwide Product Safety; [contact])

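### Sections 6.2.2 and 8.1.1.8 take a dosed patient who would miss the surgical window off trial, while other sections keep that patient in follow-up and in the analysis; read literally, DFS and OS need not be collected.

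*Combined protocol and SAP*

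**What the plan says.** The exit rule stands in Section 6.2.2, under other allowed dose interruptions, and again in 8.1.1.8. If any pembrolizumab delay makes surgery on days 56-77 from first dose impossible, "then patient will go off trial and go directly to surgery".

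Other sections treat a patient who stops treatment differently:

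- **1.0** sets the duration of participation: "Until 5 years post-surgical resection, death, or study closure".
- **6.5**: "A participant must be discontinued from study treatment but continue to be monitored in the study for any of the following reasons". One listed reason is "Unacceptable adverse experiences as described in" Section 6.2.2; noncompliance and administrative reasons are also listed.
- **7.1, footnote j**: patients "come off study 5 years post-surgery, if cancer recurs, or if patient withdraws consent". A missed surgical window is not listed. The footnote adds that survival follow-up runs on to year 5 after recurrence, or after withdrawal from treatment only.
- **8.1.2.5.3** continues tumor imaging after treatment stops without progression.
- **8.1.5.3.2**: "Subjects who discontinue trial treatment for a reason other than disease progression will move into the Follow-Up Phase".
- **6.6** puts every patient who received a first dose into the analysis.

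Section 3.2 measures DFS and OS from the first dose. On safety, 6.7 item 5 gives as a ground for termination: "If patient deaths or excessive toxicity attributed to the investigational drug are seen in the 30 days following surgery", with an attributed 30-day post-operative death rate of 5% or more as unacceptable. Section 8.2.6 discontinues the trial for any pembrolizumab-related death. Section 8.2 states: "Investigators are not obligated to actively seek AE or SAE or other reportable safety events in former study participants".

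**The concern.** The exit wording is the only instruction written for this specific event, and it is what a site will act on. Outcomes that a site stops collecting cannot be recovered at analysis. A dosed patient sent off trial would remain in the 6.6 analysis set with DFS and OS cut off at about the time of surgery.

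The loss need not be random. The 6.2.2 paragraph opens with interruptions unrelated to treatment toxicity, but the exit sentence covers any delay, and 8.1.1.8 repeats it without that opening. Table 3 withholds doses for immune-related events, and 8.2.6 itself foresees toxicity pushing surgery beyond the window. The patients at risk of being lost may therefore be those who tolerated the drug worst.

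The second stake is safety. The 6.7 item 5 rule needs 30-day post-operative outcomes in every dosed patient who has surgery, so it matters whether the reporting rules still reach a patient who has left the trial.

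**Working it through.** **1. The plan's own design figure.** Section 9.2 stops at 0/15 and calls 2 or more of 33 promising. The probability of a positive result at true rate p is

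1 - (1-p)^15 - 15p(1-p)^14 x (1-p)^18.

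- p = 0.01: 1 - 0.8601 - 0.1087 = 0.0312, within the stated 0.10.
- p = 0.15: 1 - 0.0874 - 0.0124 = 0.9002, the stated 90%.

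The design reproduces, and nothing below touches it.

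**2. Is the same patient both out and in?** Take a patient with one dose, a hold that rules out surgery by day 77, and then resection. Under 6.2.2 and 8.1.1.8 the patient is off trial. Under 1.0 participation runs to 5 years. Under 8.1.5.3.2 a patient who stops treatment without progression enters follow-up. Under footnote j no listed reason to come off study has occurred. Under 6.6 the patient is analysed. Section 6.5 does not name a missed window, but it reaches this patient through its adverse-experience, noncompliance or administrative reasons. These statements cannot all hold if off trial means out of the study; they can if it means off study treatment.

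**3. Are 30-day post-operative deaths still reportable?** Inputs: nominal doses on days 0, 21 and 42; end of treatment is the day of the last dose (8.1.5.3.1); deaths from any cause are reportable for 90 days after cessation (8.2.3.1). Cover ends on day L + 90 for a last dose on day L. Surgery on day s needs cover to s + 30, so cover is complete if s is at most L + 60.

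| Doses given | Last dose (L) | Cover ends (L + 90) | Latest surgery with full cover (L + 60) |
|---|---|---|---|
| 1 | 0 | 90 | 60 |
| 2 | 21 | 111 | 81 |
| 3 | 42 | 132 | 102 |

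Surgery on days 56-77 needs cover to days 86-107. After two or three doses that is always met. After one dose the shortfall is s - 60 days once s passes 60: 107 - 90 = 17 days at day 77. If surgery slips past day 77, two-dose patients are short only after day 81. This assumes that no new anticancer therapy cuts the window to 30 days, and that the planned resection is not counted as one.

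**4. What one missed death could do.** Section 8.2.6 acts on a single related death. Under 6.7 item 5, one attributed death reaches 5% in up to 20 operated patients (1/20 = 5.0%; 1/15 = 6.7%). At the end of stage 1, losing an exit patient who died would turn 1/15 into 0/14.

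**5. Survival, as illustration only.** Suppose a fraction d exits and is censored at surgery, those who stay have 5-year survival S, and exits have hazard ratio HR. Ignoring deaths before surgery, Kaplan-Meier estimates about S, while the truth is (1-d)S + d x S^HR. The overstatement is d(S - S^HR). Values of S come from Section 4.2.1; d and HR = 2 are assumptions.

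| S | d = 5% | d = 10% | d = 20% | SE, sqrt(S(1-S)/33) |
|---|---|---|---|---|
| 42% | 1.2 | 2.4 | 4.9 | 8.6 |
| 57% | 1.2 | 2.5 | 4.9 | 8.6 |
| 68% | 1.1 | 2.2 | 4.4 | 8.1 |

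Entries are percentage points. With HR = 1 the overstatement is zero.

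**The case against.** The best defence is that the plan, read as a whole, already gives the right answer. The exit sentence sits in a paragraph about dose interruption and return to study therapy, so off trial is most naturally off trial therapy. Several safeguards do not depend on trial status or apply on early exit:

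- Section 8.1.5.3.1 follows adverse events above Grade 1 to resolution or new anticancer therapy.
- Section 8.1.4.1 requires final-visit activities and adverse event follow-up on early discontinuation.
- Section 8.2.6 holds the study for review when toxicity pushes surgery out of the window.
- Drug-related serious events that come to an investigator's attention are reportable at any time.
- Attribution under 6.7 item 5 rests with the treating oncologist and surgeon, who would ordinarily know of a post-operative death.

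Most of this stands, and it confines the safety concern. A reader might infer that 30-day post-operative deaths in exit patients generally go uncollected. The documents do not support that: the 90-day any-cause rule runs from the last dose. A wider gap requires a site to treat an off-trial patient as a former participant under 8.2, an equation that no section makes, although the wording leaves room for it. Nor would a missed death always change the outcome: if another related death is already on record, 8.2.6 has stopped the trial.

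It is also fair that a 30-day vital-status check is a new request. The legible text shows no scheduled 30-day post-operative contact for any patient, and the flow chart is only partly legible.

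The defence does not remove the survival problem. DFS and OS have no fixed-window backstop, and the favourable reading must be inferred against an explicit instruction written twice.

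**Conclusion.** The contradiction is real and should be corrected. Its main consequence is that, on a literal reading, disease and survival follow-up of some dosed patients need not be collected although DFS and OS include them. The loss may be informative. Its size cannot be stated, because the documents give no exit rate. The survival table rests on assumed exit rates, a hazard ratio of 2 and censoring at surgery; even then the effect is 1.1 to 4.9 points against a standard error above 8, on secondary endpoints. It should not be read as an estimate of bias in this trial.

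The safety gap is narrow. On nominal dose days and surgery by day 77, it covers one-dose patients operated on after day 60, and becomes wider only if a site reads off trial as former participant.

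A reader might also infer that the primary endpoint is compromised. It is not: 6.6 keeps every dosed patient, and the default to non-response applies only to those who do not have surgery.

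**What to change.** 1. In 6.2.2 and 8.1.1.8, state that the patient leaves study treatment only and, subject to consent, stays in post-operative safety, DFS and OS follow-up. This reconciles them with 1.0, 6.5, 6.6, 8.1.2.5.3 and 8.1.5.3.2.
2. Align footnote j by naming this exit and saying that follow-up continues.
3. In 6.7 item 5, state that the count includes every dosed patient who has surgery, and record vital status 30 days after surgery whatever the date of the last dose.
4. Report how many patients left under this rule.

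The cost is amendment wording in a few places, one vital-status check per operated patient and continued follow-up of a few patients. Sample size, two-stage design and primary analysis are unchanged. No dosing or clinical rule is proposed.

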6.3 Randomization or Treatment Allocation

This is an open-label trial; therefore, the P.I., treating investigator and subject will know the treatment administered.

6.4 Concomitant Medications/Vaccinations (allowed & prohibited)

Medications or vaccinations specifically prohibited in the exclusion criteria are not allowed during the ongoing trial. If there is a clinical indication for one of these or other medications or vaccinations specifically prohibited during the trial, discontinuation from trial therapy or vaccination may be required. The final decision on any supportive therapy or vaccination rests with the treating investigator and/or the participants' primary physician.

6.4.1 Acceptable Concomitant Medications

All treatments that the treating investigator considers necessary for a participant's welfare may be administered at the discretion of the investigator in keeping with the community standards of medical care. All concomitant medication will be recorded on the case report form (CRF) including all prescription, over-the-counter (OTC), herbal supplements, and IV medications and fluids. If changes occur during the trial period, documentation of drug dosage, frequency, route, and date may also be included on the CRF.

All concomitant medications received within 28 days before the first dose of trial treatment and 30 days after the last dose of trial treatment should be recorded. Concomitant medications administered after 30 days after the last dose of trial treatment should be recorded for SAEs and Events of Clinical Interest (ECIs) as defined in [Section 8.2](#).

6.4.2 Prohibited Concomitant Medications

Participants are prohibited from receiving the following therapies during the Screening and Treatment Phase (treatment phase refers to the time between the first dose of pembrolizumab and the date of surgery) of this trial:

- Antineoplastic systemic chemotherapy or biological therapy
- Immunotherapy not specified in this protocol
- Investigational agents other than pembrolizumab

- Radiation therapy
- Live vaccines within 30 days prior to the first dose of study treatment and while participating in the study. Examples of live vaccines include, but are not limited to, the following: measles, mumps, rubella, varicella/zoster, yellow fever, rabies, BCG, and typhoid vaccine. Seasonal influenza vaccines for injection are generally killed virus vaccines and are allowed; however, intranasal influenza vaccines (eg, FluMist®) are live attenuated vaccines and are not allowed.
- Systemic glucocorticoids for any purpose other than to modulate symptoms from an event of clinical interest of suspected immunologic etiology. The use of physiologic doses of corticosteroids may be approved after consultation with the P.I.

Participants who, in the assessment by the investigator, require the use of any of the aforementioned treatments for clinical management should be removed from the study. All treatments that the treating investigator considers necessary for a participant's welfare may be administered at the discretion of the Investigator in keeping with the community standards of medical care.

Medications or vaccinations specifically prohibited in the exclusion criteria are not allowed during the ongoing study. If there is a clinical indication for any medication or vaccination specifically prohibited during the study, discontinuation from study therapy or vaccination may be required. The final decision on any supportive therapy or vaccination rests with the treating investigator and/or the participant's primary physician. However, the decision to continue the participant on study treatment requires the mutual agreement of the treating investigator, the P.I. and the participant.

Antibiotic therapies may be required by some participants during the study, but would avoid as safely able as this may affect pembrolizumab response and fecal flora.[41, 42] Antibiotic choice: Different classes of antibiotics have been shown to disrupt the microbiome and potentially interfere with normal host immune function to varying degrees. If equally indicated amoxicillin is the preferred antibiotic as it minimally alters gut flora. Clindamycin is the most detrimental antibiotic and should be avoided if possible.[43] Beta-lactams (other than amoxicillin) and fluoroquinolones broadly should be avoided if possible as well.[44]

There are no prohibited therapies during the Post-Treatment Follow-up Phase.

6.4.3 Rescue Medications & Supportive Care

Participants should receive appropriate supportive care measures as deemed necessary by the treating investigator. Suggested supportive care measures for the management of AEs with potential immunologic etiology are outlined along with the dose modification guidelines in [Section 6.2.2](#), [Table 3]. Where appropriate, these guidelines include the use of oral or IV treatment with corticosteroids, as well as additional anti-inflammatory agents if symptoms do not improve with administration of corticosteroids. Note that several courses of steroid tapering may be necessary as symptoms may worsen when the steroid dose is decreased. For each disorder, attempts should be made to rule out other causes such as metastatic disease or bacterial or viral infection, which might require additional supportive care. The treatment

guidelines are intended to be applied when the treating investigator determines the events to be related to pembrolizumab.

Note: If after the evaluation of the event, it is determined not to be related to pembrolizumab, the treating investigator does not need to follow the treatment guidance. Refer to [Table 3] in [Section 6.2.2](#) for guidelines regarding dose modification and supportive care.

It may be necessary to perform conditional procedures such as bronchoscopy, endoscopy, or skin photography as part of evaluation of the event.

